7.2.7 Safety Considerations

Several safety concerns regarding the infusion of large numbers of retrovirally-modified tumor reactive T cells have been addressed in previous clinical studies.

CAR transduced human T cells have been administered to humans in several clinical trials. Pule, et al. engineered human T cells to express a CAR directed to the disialoganglioside GD2, a tumor associated antigen expressed by human neuroblastoma cells¹⁶. These CAR transduced cells were administered to eleven children between the ages of 3 and 10, all of whom had metastatic neuroblastoma. There were no adverse effects attributable to the genetically modified CAR T cells in the eleven subjects that were followed for up to two years following cell infusion. Two patients exhibited an objective response. Persistence of the transduced cells was greater when the CAR were inserted into EBV specific cytolytic T lymphocytes than when the CAR were inserted into T cells that were activated by an anti- CD3 monoclonal antibody.

The NCI treated patients with B cell lymphomas utilizing lymphocytes transduced with a retrovirus encoding a CAR that recognizes the CD19 molecule^{30,63-65}. As expected by the targeting of CD19, the protocol was associated with elimination of normal B cells. One patient required ICU

support for toxicity similar to tumor lysis syndrome and a second patient treated on this study died prior to response evaluation from H1N1 influenza infection. This death is possibly related to the research, but is not related to the anti-CD19 CAR transduced cells.

A patient with metastatic colorectal cancer was treated with 10^{10} autologous T cells transduced with the retrovirus encoding an anti-Her-2 CAR. This patient developed respiratory distress and died four days later²⁹. This toxicity was apparently due to a previously unrecognized ability of this CAR to recognize Her-2 expressed on lung epithelial cells although the exact explanation for the toxicity is not clear. As the EGFRvIII protein is tumor specific normal cell recognition is not expected. In addition, as previously described, multiple EGFRvIII vaccine trials have been reported and no significant vaccine-related toxicities have been observed⁶⁶⁻⁶⁸.

The expansion of tumor reactive cells is a desirable outcome following the infusion of antigen reactive T cells and this expansion could mimic the clonal expansion of a transformed lymphocyte. The transfer of gene modified cells has a significant risk for malignant transformation in this patient population. While the risk of insertional mutagenesis is a known possibility using retroviral vectors, this has only been observed in the setting of patients with primary immunodeficiencies using retroviral vector-mediated gene transfer into CD34+ bone marrow cells. In the case of retroviral vector-mediated gene transfer into mature T cells, there has been no evidence of long-term toxicities associated with these procedures since the first NCI sponsored gene transfer study in 1989. Although continued follow-up of all gene therapy patients will be required, data suggest that the introduction of retroviral vectors transduced into mature T cells is a safe procedure. The NCI risk of insertional mutagenesis is extremely low, and the proposed protocol follows all current FDA guidelines regarding testing and follow up of patients receiving gene transduced cells.

7.3 Study Purpose/Rationale

The goal of this protocol is to transfer PBL transduced with genes encoding a CAR that recognizes an EGFRvIII, tumor-specific antigen into patients with WHO Grade IV malignant glioma. The CAR used will be targeted to a tumor-specific mutation, EGFRvIII, which is expressed on a subset of patients. Normal PBLs derived from patients with WHO Grade IV malignant glioma will be genetically engineered with a viral vector encoding the CAR and infused into newly diagnosed malignant glioma patients with the aim of mediating regression of their tumors. In a recent trial, EGFRvIII CARs were administered to recurrent malignant glioma patients. The starting EGFRvIII CAR dose for this study (ExCeL) was shown to be safe in that recent study in patients with recurrent malignant glioma.

Correlative studies are also proposed to document the expansion, functional persistence,^{19,69} and trafficking⁷⁰⁻⁷² to tumor of adoptively transferred EGFRvIII CARs as these have been the correlates of successful therapy for other investigators.

8 OBJECTIVES AND ENDPOINTS

Table 2. Objectives and Endpoints

	Objective	Endpoint	Analysis
Primary	Determine the MTD of a single IV infusion of EGFRvIII CAR T cells in patients with newly-diagnosed WHO Grade IV malignant glioma.	MTD	See Section 15.4
Key Secondary	To determine the DLT of a single IV infusion EGFRvIII CAR T cells in patients with newly-diagnosed WHO Grade IV malignant glioma.	DLT	See Section 15.5
Exploratory	To determine if EGFRvIII CARs transferred into patients with WHO Grade IV malignant glioma expand.	Median number of EGFRvIII CARs in peripheral blood and KI67	See Section 15.6
Exploratory	To determine if EGFRvIII CARs persist and remain functional in the periphery.	Median number of EGFRvIII CARs by tetramer and functional assays	See Section 15.6

Exploratory	To assess whether EGFRvIII CARs traffic to tumor site.	Median proportion of injected ¹¹¹ In-labeled EGFRvIII CARs present in tumor	See Section 15.6
Exploratory	To describe the survival experience of patients treated with EGFRvIII CAR T cells.	Median survival	See Section 15.6
Exploratory	To describe the progression-free survival experience of newly-diagnosed, EGFRvIII-expressing WHO Grade IV malignant glioma patients treated with EGFRvIII CAR T cells.	Proportion of patients alive without disease progression 6 months after EGFRvIII CAR treatment	See Section 15.6

9 INVESTIGATIONAL PLAN

9.1 Study Design

Treatment Plan

Following consent, subjects who are part of the dose escalation cohort will be assigned into the appropriate dose-escalation cohorts. Patients will undergo a 2-4 hour leukapheresis to harvest PBMCs for the generation of EGFRvIII CAR T cells prior to beginning RT and concurrent TMZ. T cells will be isolated from the patient's PBMCs and transduced to express CARs. Briefly, PBMC will be stimulated with OKT3 (anti-CD3 mAb) and transduced on RetroNectin® coated plates. Transduced cells will be expanded in IL-2 for 14 days.

Patients will then complete approximately 6 weeks of standard of care RT and concurrent TMZ at a targeted dose of 75 mg/m²/d. Patients whose blood counts do not meet eligibility within 6 weeks of completing standard of care RT and concurrent TMZ will be withdrawn from the study before initiation of TMZ treatment and replaced. Patients who appear to have progressive disease following radiation may actually have pseudoprogression due to the radiation and will be allowed to continue to cycle 1 of (dose intensified) DI TMZ in order to not be excluded from the study prematurely, at the discretion of the treating physician. If the patient is determined to have progressive disease, the patient may be eligible for the INTERCEPT study (INTRacerebral EGFR-vIII Chimeric Antigen Receptor Gene-Modified T Cells for PaTients with Recurrent GBM, Pro00083828). If the patient is determined to be eligible for the INTERCEPT study (Pro00083828), the cells extracted from leukapheresis while they were on this study, ExCeL, will be used to create the CAR T cells for administration in the INTERCEPT study.

Patients without definitive disease progression who remain eligible will then receive up to 3 cycles of dose-intensified (DI) TMZ at 50-100 mg/m²/day. Each full cycle of DI TMZ is 50-100 mg/m²/day for 21 days every 28 days, at the discretion of the treating physician. The purpose of the DI TMZ cycles is to achieve grade 3 lymphopenia. If the patient is able to tolerate the TMZ, they will receive 3 full cycles of DI TMZ prior to receiving the CAR T cells. If the patient is unable to complete the 3 cycles of DI TMZ, but has achieved grade 3 lymphopenia, they may receive CAR treatment at the discretion of the study PI and/or treating oncologist. If the patient's grade 3 lymphopenia subsides during the ~2 weeks it takes to produce the CAR T cells and before the scheduled receipt of CAR T cells, the treating physician has the discretion to re-initiate TMZ to re-establish grade 3 lymphopenia. If the patient is unable to tolerate the 3 full cycles of TMZ and does not reach grade 3 lymphopenia, or if the CAR-specific T cells do not meet release criteria, the patient will be withdrawn before CAR treatment and replaced.

Two weeks prior to CAR T cell administration, the patient must be on stable or decreasing steroids (≤ 4 mg/day). If patients are decreasing steroid use, once they are at 2 mg/day, they may be supplemented with hydrocortisone, at the discretion of the treating oncologist.

At least 48 hours after the patient's last dose of TMZ, the total dose of EGFRvIII CAR T cells will be delivered intravenously. If sufficient CAR-specific T cells cannot be generated to meet the targeted assigned dose within the dose-escalation portion of the study, the patient will be treated at a lower pre-defined dose level using available CAR-specific T cells and replaced in the assigned higher dose. The administered dose will be the highest defined dose level for which there are sufficient CAR-specific T cells available. Within the expanded cohort, if sufficient CAR-specific T cells can't be generated to meet the MTD dose, all available T cells will be administered.

Blood samples for immune monitoring (9 yellow, 1 red) will be drawn prior to EGFRvIII CAR infusion, 1, 5, 10, and 28 days after the infusion, then 3 and 6 months, then yearly until progression (or death or lost to contact). The return visits for immune monitoring at the 3 months, ~6 months, and ~yearly will

coincide with standard of care clinic visits. A portion of the immune monitoring blood sample will be used for RCR PCR per the FDA prior to EGFRvIII CAR infusion, and at 3, 6 and 12 months during standard of care clinic visits. Lastly, blood for evaluation of CRS (1 red, 1 purple top – 3mLs each) will be drawn prior to cell infusion, 1 and 4 hours after infusion, and on days 1, 2, 5, 10, and at approximately 28 days. Measurements for CRS include IL-2, IL-6, TNF α , IFN γ , GM-CSF, and C-reactive protein (CRP).

Patients will return to clinic approximately 28 days following the EGFRvIII CAR T cell infusion to be evaluated for cycles of standard of care 5-day TMZ at 150-200 mg/m²/day for the first 5-day cycle, followed by 200 mg/m²/day (if tolerated by the patient) for 5-days every 28 days at the discretion of the treating oncologist. This will result in an approximately > 30-day delay between the last TMZ administration prior to EGFRvIII CAR T cell infusion and the TMZ cycle initiated after the study drug infusion. This delay in the TMZ cycle after the CAR T cell infusion is done in an attempt to decrease the chance of study drug washout by TMZ.

Tumor progression will be documented histologically, unless there are clinical contraindications, to exclude inflammatory responses presenting as radiographic or clinical changes, which could indicate a potentially toxic or therapeutic responses and not tumor progression. If tissue is obtained through the Duke Brain Tumor Center Biorepository IRB# Pro00007434, it will be used to confirm tumor progression histologically, and to assess immunologic cell infiltration and EGFRvIII antigen escape at the tumor site. Patients will be eligible for additional adjuvant therapy at the time of tumor progression.

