An expanded cohort of a total of 12 patients will be enrolled at the MTD of EGFRvIII CAR T cells in order to obtain a more precise estimate of the probability of unacceptable toxicity. This cohort will also have the cells radiolabeled with ^{111}In to track their distribution. Briefly, CARs will be counted and re-suspended in PBS. $4\text{-}6 \times 10^8$ cells will be labeled with 500 micro Ci of ^{111}In . The cells will be washed and mixed with cold CARs to achieve the desired cell dose with a total of 500 μCi of ^{111}In . The labeled CARs will be infused into the patient through an intravenous catheter within the Ambulatory Bone Marrow Transplant (BMT) Unit. Distribution of ^{111}In -labeled EGFRvIII CARs will be evaluated at 1, 2, and 3 days post-infusion using whole body planar imaging followed by SPECT/CT, when indicated.

In the rare event that a sufficient amount of CAR-specific T cells cannot be generated for a patient's intended dose within the dose-escalation portion of this study, the patient will be treated at a lower pre-defined dose level using available CAR-specific T cells. If this patient experiences a DLT, data will be carefully reviewed to determine its impact upon dose escalation and future patient treatment. If this situation occurs with the expanded cohort, all available cells will be administered.

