9.4 Definition of Evaluable Subjects, On Study, and End of Study

While all patients who received any EGFRvIII CAR T cells will be included in safety summaries for the purposes of monitoring and reporting of adverse events to appropriate agencies, patients evaluable for determination of the MTD will include:

- Patients who receive the entire CARs infusion (i.e. the infusion is not stopped prematurely), and 2) have 4 weeks of follow-up for adverse events after the infusion
- Patients who receive the entire CARS infusion (i.e. the infusion is not stopped prematurely) and terminated follow-up prematurely during the 4 week follow-up period after having experienced a DLT.
- Patients who terminate infusion before completion due to a DLT

For the efficacy analyses, evaluable patients will include two groups of patients: all patients, and the subgroup of patients who receive EGFRvIII CAR. Once a patient's eligibility is confirmed after completion of XRT/TMZ, that subject will be considered "on study". The rationale for taking a patient off study will be documented. Please see Section 12.7 for information on patient withdrawals.

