10.4.2 Release Criteria for EGFRvIII CARs

Tests performed on the final product:

Table 5. Release Criteria for EGFRvIII CARs

Test	Method	Limits	Result	Initials/Date
-------------	---------------	---------------	---------------	----------------------

Cell viability ¹	Trypan blue exclusion	>70%		
Total viable cell number ¹	Visual microscopic count	>1 x 10 ⁷		
Tumor reactivity ²	γ-IFN release vs. EGFRvIII antigen	>200 pg/ml		
CAR expression ²	FACS analysis of the transduced cells	PBL >10%		
Microbiological studies	Gram stain ^{1,3}	No micro-organisms seen		
	Aerobic culture ^{3,4}	No growth		
	Fungal culture ^{3,4}	No growth		
	Anaerobic culture ^{3,4}	No growth		
	Mycoplasma test ⁵	Negative		
Endotoxin	Limulus assay ¹	<5 E.U./Kg		
RCR	S+L-Assay ⁴ RCR-PCR ⁶	Negative		

In the event of a positive sterility test, after the product has been infused, the Principal Investigator or his or her designate will notify the treating physician and the patient. The FDA and IRB will be notified within 15 calendar days. The patient will be asked to be evaluated by a physician within 24 hours. If the patient has or develops a temperature >38.5 °C or clinical evidence of infection at the injection site (erythema or edema) or systemically, the patient will have samples of from the injection sites, along with blood, urine and sputum (if possible) sent for bacterial, fungal, culture and sensitivity testing and will be treated expectantly with antibiotics based on the sensitivities of the organisms identified from the immunization product and an independent infectious disease consultation will be obtained to guide further therapy. Any remaining lymphocytes will be sent for bacterial, and fungal, culture and sensitivity testing and endotoxin testing.

10.4.3 ¹¹¹In-labeled T cells

CARs are washed three times with PBS, assessed for viability, and counted. CARs are re-suspended in PBS. 4-6x10⁸ cells will be labeled with 500 micro Ci of ¹¹¹In. The cells will be washed and mixed with cold CARs to achieve the desired cell dose containing 500 micro Ci of ¹¹¹In. The cell concentration is adjusted to 2.5 x10⁷ cells per mL and resuspended in preservative free saline with 1% human serum albumin (Baxter Healthcare Corp., US License No 140 NDC0944-0490-0L) and placed into the appropriate size syringe for infusion.

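### Do expansion patients who receive fewer cells than the MTD dose make the DLT rate at the MTD unreliable?

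*Combined protocol and SAP*

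**What the plan says.** Section 9.1 treats a shortage of cells differently in the two parts of the trial. In escalation, the patient is treated at a lower defined level "using available CAR-specific T cells and replaced in the assigned higher dose". In the expansion, if enough cells cannot "be generated to meet the MTD dose, all available T cells will be administered", and Section 9.1.1 repeats this: "If this situation occurs with the expanded cohort, all available cells will be administered". Section 12.7.3 replaces patients who get no CAR cells, and those who stop the infusion early or are lost within 4 weeks without a DLT. A shortage in the expansion is not on that list.

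The expansion enrols 12 patients at the MTD "in order to obtain a more precise estimate of the probability of unacceptable toxicity" (Section 9.1.1). Section 15.7 anticipates 18 patients treated at the MTD, 6 from escalation and 12 from the expansion. Sections 15.3 and 15.5 report treatment counts and DLT proportions by dose level, with no statement on assigned or received dose. Section 15.5 names no analysis set.

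Two definitions bear on who counts. Section 9.4 lists as evaluable for the MTD "Patients who receive the entire CARs infusion (i.e. the infusion is not stopped prematurely"). The MTD Analysis Set in Section 15.1 drops patients without a DLT who did not finish the infusion intended for them. The Overall Safety Analysis Set, also in Section 15.1, takes everyone given any CAR cells.

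**The concern.** An amount set by whatever cells are available need not match any of the four dose levels, so it is unclear where the patient belongs in a table by dose level. Two readings seem possible.

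- **Reading A.** The infusion was not stopped early, so the patient counts at the MTD. If toxicity rises with dose, short patients dilute the rate.
- **Reading B.** The intended infusion in Section 15.1 means the target dose, in the way Section 9.1.1 speaks of a patient's "intended dose within the dose-escalation portion of this study". Short patients without a DLT then leave the denominator while those with a DLT stay. Inclusion depends on outcome and the rate is overstated.

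DLT is the key secondary endpoint, and a better estimate of its rate is the stated reason for the expansion. A denominator that could be settled after the DLTs are seen would be a fair worry.

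**Working it through.** **1. The plan's own precision figure.** Table 7 gives a 95% half-width of 0.047 at a DLT rate of 0.25. With n = 18 the Wald half-width is 1.96 × √(0.25 × 0.75 / 18) = 0.200, so the table is not reproduced. Its value is close to 1.96 × √0.1875 / 18 = 0.0471, which suggests division by 18 instead of √18. That is a separate matter. The yardstick used here is 0.200.

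**2. Which count the text supports.**

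| Place | How non-completion or counting is framed |
|---|---|
| 9.1.1, text after Table 4 | infusion ended early by the patient |
| 9.4 | entire infusion explained as not stopped early |
| 12.7.3 | infusion ended early |
| 15.1, MTD set | intended infusion not completed |
| 15.1, Overall Safety set | anyone given any CAR cells |
| 15.7 | all 12 expansion patients among the 18 |

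The first three places all mean a stopped infusion, and the fourth reads most naturally as the same rule. In the expansion, giving all available cells is the prescribed administration, so a patient who receives them has completed the intended infusion. Sections 9.4 and 15.1 also limit these definitions to determining the MTD, which is settled before the expansion starts. What remains is the Overall Safety set and the count of 18, and both give reading A.

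**3. Size under reading A.** Let n = 18, m the number of short patients, p the DLT risk at full dose and q the risk when short. The 18 are treated as unselected. The documents give no shortage rate. Section 9.1.1 calls the event rare when describing escalation, so m = 1 or 2 is taken as plausible and m = 4 as high. The value p = 0.25 is the top of Table 7, and q is an assumption.

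Bias = −m(p − q)/18.

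| m | p = 0.25, q = 0.05 | p = 0.25, q = 0 | p = q = 0.25 |
|---|---|---|---|
| 1 | −0.011 | −0.014 | 0 |
| 2 | −0.022 | −0.028 | 0 |
| 4 | −0.044 | −0.056 | 0 |

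For m = 2 with p from 0.15 to 0.30 and q from 0 to 0.10, the range is −0.006 to −0.033.

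**4. Size under reading B.** Bias = E[(X + Y)/(18 − m + Y)] − p, with X ~ Bin(18 − m, p) and Y ~ Bin(m, q), by enumeration. For m = 2, p = 0.25 and q = 0.05:

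0.9025 × 0.25 + 0.095 × 5/17 + 0.0025 × 6/18 = 0.2544, a bias of +0.004.

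For m = 1 and m = 4 it is +0.002 and +0.010. With q = p = 0.25 it is +0.010, +0.022 and +0.048 for m = 1, 2 and 4. With q = 0 it is zero.

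**5. One possible data set.** Take 16 full-dose and 2 short patients, with 4 DLTs of which one is in a short patient.

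| Count | Rate | Exact 95% CI |
|---|---|---|
| Reading A, 4/18 | 22.2% | 6.4–47.6% |
| Reading B, 4/17 | 23.5% | 6.8–49.9% |
| Full dose only, 3/16 | 18.8% | 4.0–45.6% |

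The intervals overlap almost entirely. Readings A and B both lie above the full-dose rate here, so their opposite directions hold only in expectation, and only for 0 < q < p.

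**The case for a change.** The strongest case for a change is that the authors saw the shortage problem in escalation and wrote a rule for it, then left the expansion without one. Section 15.7 only anticipates 18 patients, which is a projection and not a denominator rule. Section 15.1 does not repeat the explanation given in Section 9.4. The remark that shortage is rare is attached to escalation, while the expansion doses at the MTD, possibly the highest level. The dose given also has no stated floor at any level, because the limits in Table 5 on "Total viable cell number" and on "FACS analysis of the transduced cells" are set for product release. No output of cells/kg received is planned, and adding one would cost little.

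Part of this stands. Sections 15.3 and 15.5 would be clearer if they said assigned or received and named the analysis set, and the two evaluability phrases could match. The absent floor matters little, because the column q = 0 in the working already covers a dose too small to cause any DLT.

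Making received dose the main estimate is no clear gain. Counting everyone assigned to the MTD is a legitimate target for an autologous product whose yield varies. Excluding short patients is unbiased only if shortage is unrelated to DLT risk, and it needs a tolerance around the MTD dose that would itself have to be chosen. With 2 patients removed, the half-width at 0.25 rises from 0.200 to 1.96 × √(0.1875/16) = 0.212.

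The Table 3 footnote caps level 4 in total cells while doses are set in transduced cells/kg. Those passages should be reconciled, but the cap is a planned part of that level and does not bear on how short patients count.

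**Conclusion.** No change to the plan follows. This is a gap in detail that analysts fill sensibly: they count all treated patients, apply the same rule with or without a DLT, and report the cells received by anyone who fell short. With 1 or 2 short patients and assumed risks of 0.25 and 0.05, the descriptive rate moves by 0.011 to 0.022, at most about one ninth of the 0.200 half-width (0.022/0.200 = 0.11). Even 4 short patients of 12 move it by 0.044, about a fifth. MTD selection is unaffected, and Section 15.5 is a tabulation with no decision attached.

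The conclusion rests on shortage being uncommon in the expansion, as Section 9.1.1 says of escalation, and on non-completion in Section 15.1 meaning a stopped infusion, as it does in Sections 9.1.1, 9.4 and 12.7.3. If shortage proved common, the dose actually received would deserve more weight when the rate is interpreted.
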